#### **7.12 Changes in the Statistical Analysis Plan**

No additional/modified FAS or per-protocol populations will be defined. No interim analysis for Part 1 will be performed.

**Appendix A Criteria for Identification of Markedly Abnormal Laboratory Values**  
**Hematology – Criteria for Markedly Abnormal Values (SI units)**

Parameter	Unit	Low Abnormal	High Abnormal
Hemoglobin	Both	$< 0.8 \times \text{LLN}$	$> 1.2 \times \text{ULN}$
Hematocrit	Both	$< 0.8 \times \text{LLN}$	$> 1.2 \times \text{ULN}$
RBC count	Both	$< 0.8 \times \text{LLN}$	$> 1.2 \times \text{ULN}$
WBC count	Both	$< 0.5 \times \text{LLN}$	$> 1.5 \times \text{ULN}$
Platelet count	Conventional	$< 75 \times 10^3/\mu\text{L}$	$> 600 \times 10^3/\mu\text{L}$
	SI	$< 75 \times 10^9/\text{L}$	$> 600 \times 10^9/\text{L}$
Prothrombin time/international normalized ratio	Both	--	$> 1.5 \times \text{ULN}$
Activated partial thromboplastin time	Both	--	$> 1.5 \times \text{ULN}$

LLN=lower limit of normal, RBC=red blood cell, ULN=upper limit of normal, WBC=white blood cell.

**Serum Chemistry – Criteria for Markedly Abnormal Values (SI units)**

Parameter	Unit	Low Abnormal	High Abnormal
ALT	Both	--	$> 3 \times \text{ULN}$
AST	Both	--	$> 3 \times \text{ULN}$
GGT	Both	--	$> 3 \times \text{ULN}$
Alkaline phosphatase	Both	--	$> 3 \times \text{ULN}$
Calcium	Conventional	$< 7.0 \text{ mg/dL}$	$> 11.5 \text{ mg/dL}$
	SI	$< 1.75 \text{ mmol/L}$	$> 2.88 \text{ mmol/L}$
Chloride	Conventional	$< 75 \text{ mEq/L}$	$> 126 \text{ mEq/L}$
	SI	$< 75 \text{ mmol/L}$	$> 126 \text{ mmol/L}$
Total bilirubin	Conventional	--	$> 2.0 \text{ mg/dL}$
	SI	--	$> 34.2 \mu\text{mol/L}$
Albumin	Conventional	$< 2.5 \text{ g/dL}$	--
	SI	$< 25 \text{ g/L}$	--
Total protein	Both	$< 0.8 \times \text{LLN}$	$> 1.2 \times \text{ULN}$
Creatinine	Conventional	--	$> 2.0 \text{ mg/dL}$
	SI	--	$> 177 \mu\text{mol/L}$
Blood urea nitrogen	Conventional	--	$> 30 \text{ mg/dL}$
	SI	--	$> 10.7 \text{ mmol/L}$
Sodium	Conventional	$< 130 \text{ mEq/L}$	$> 150 \text{ mEq/L}$
	SI	$< 130 \text{ mmol/L}$	$> 150 \text{ mmol/L}$

**Serum Chemistry – Criteria for Markedly Abnormal Values (SI units)**

Parameter	Unit	Low Abnormal	High Abnormal
Potassium	Conventional	<3.0 mEq/L	>6.0 mEq/L
	SI	<3.0 mmol/L	>6.0 mmol/L
Glucose	Conventional	< 50 mg/dL	>350 mg/dL
	SI	< 2.8 mmol/L	>19.4 mmol/L
Bicarbonate	Conventional	<8.0 mEq/L	--
	SI	<8.0 mmol/L	--
Creatine kinase	Conventional	--	>5 × ULN
	SI	--	>5 × ULN
Total Cholesterol	Conventional	--	>300 mg/dL
	SI	--	>7.72 mmol/L
Triglycerides	Both	--	>2.5 × ULN
LDL Cholesterol	Conventional	< 50 mg/dL	>160 mg/dL
	SI	<1.30 mmol/L	>4.14 mmol/L
HDL Cholesterol	Conventional	<40 mg/DL	>60mg/DL
	SI	<1.04 mmol/L	>1.55 mmol/L
Alpha-1-Acid Glycoprotein	Conventional	<47mg/DL	>125 mg/DL

ALT=alanine aminotransferase, AST=aspartate aminotransferase, GGT=γ-glutamyl transferase, LLN=lower limit of normal, ULN=upper limit of normal.

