#### 13.1.3.2 Other Safety Endpoints

Absolute values and changes from Screening/Baseline for clinical laboratory tests, vital signs, and ECGs will be summarized by treatment group for each part of the study using descriptive statistics. Clinical laboratory test, vital sign, CCI [REDACTED] and ECG results that are outside the normal ranges and potentially clinically significant will be flagged and tabulated. The number and percentage of subjects with clinical laboratory test, vital sign, weight/BMI, and ECG parameter values that meet Takeda's predefined criteria for markedly abnormal values at least once postdose will be summarized by treatment and part of the study. Physical examination findings will be listed by subject and treatment group for each part of the study.

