**Diagnostic Screening**

Serum	Urine (a)
HIV	Drug screen including amphetamines, barbiturates,
HBsAg and anti-HCV	benzodiazepines, cannabinoids, cocaine, opiates, alcohol, and
HCV RNA detection by qPCR (e)	cotinine
hCG (for pregnancy) (f)	hCG (for pregnancy) (f)

aPTT= activated partial thromboplastin time, FSH=follicle-stimulating hormone, GGT=γ-glutamyl transferase, HDL=high-density lipoprotein, LDL=low-density lipoprotein, PT=prothrombin time, RBC=red blood cell; WBC=white blood cell.

(a) If urine cannot be collected at the time of the Screening Visit or other Visits due to the subject's cooperation or because the subject is wearing a diaper, it is acceptable for the subject to continue in the study and the reason should be documented in the source document.

(b) Only if dipstick results are positive.

(c) For diagnostic purposes in female subjects only.

(d) In female patients only

(e) Subjects who are positive for hepatitis C Ab should return to the clinic for an unscheduled visit to provide a blood sample for HCV qPCR.

(f) Only for female subjects of childbearing potential. If urine cannot be collected at Visit 2, the reason should be documented in the source document and the results of the serum pregnancy test obtained at Visit 1 must be confirmed to be negative by the investigator prior to randomization. An additional serum hCG pregnancy test will be performed at the Final Visit.

All laboratory test parameters will be displayed in individual subject data listings in both SI units and conventional (CV) units. For test results not in SI units, the conversion to SI units will be done in derived analysis data sets using the known conversion factors. If necessary, SI units from the central laboratory may be converted to Takeda's preferred SI units in the derived dataset. All summaries and analyses will be based on the values using these preferred SI units.

Only observations within 7 days of the last dose of study drug will be included in the tables. No inferential statistics will be presented unless otherwise stated.

Descriptive statistics (N, mean, SD, median, minimum, and maximum) for the observed and change from baseline values will be presented for Parts 1 and 2 separately. Study baseline defined in Section 7.1.1 will be used for change from baseline in each part of the study. Note that character urinalysis tests will only be listed.

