Laboratory Markedly Abnormal Values (MAVs), identified by the criteria defined in [Appendix A](#), will be tabulated. If a subject has a MAV for a particular laboratory test, all visits for that subject for that parameter will be listed. The number and percentage of subjects with at least 1 post-dose markedly abnormal laboratory test result will be summarized. The mapping of the subjects who meet the MAV criteria will be listed as a table. All observations, including ones at unscheduled visits, will be included in the MAV evaluation and summaries if MAV criteria are satisfied.

All clinical laboratory data will be presented in both SI and conventional units in data listings.

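### The 40–60 mg/dL HDL band in SAP Appendix A is likely to inflate the laboratory markedly-abnormal-value percentage with background HDL, and alpha-1-acid glycoprotein has no SI limits

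*SAP*

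**What the plan says.** The secondary safety endpoint (Protocol 5.2.2, SAP 5.2) is the percentage of subjects with at least one markedly abnormal value (MAV) in laboratory tests, vital signs or ECG after TAK-935. For laboratory tests, SAP 7.11.2 states: "The number and percentage of subjects with at least 1 post-dose markedly abnormal laboratory test result will be summarized". Unscheduled samples count. No normal baseline and no change from baseline is required.

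The limits are in SAP Appendix A. For HDL they read "HDL Cholesterol Conventional <40 mg/DL >60mg/DL", with SI limits "<1.04 mmol/L >1.55 mmol/L". For comparison, the LDL row reads "LDL Cholesterol Conventional < 50 mg/dL >160 mg/dL". Liver enzymes are flagged above 3 × ULN, creatine kinase above 5 × ULN, total cholesterol above 300 mg/dL, and glucose below 50 or above 350 mg/dL.

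The AAG row reads "Alpha-1-Acid Glycoprotein Conventional <47mg/DL >125 mg/DL". It is the only parameter in Appendix A with neither an SI row nor a row marked as valid for both unit systems. SAP 7.11.2 says: "All summaries and analyses will be based on the values using these preferred SI units".

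Protocol 13.1.3.2 describes another laboratory output besides the MAV summary: "results that are outside the normal ranges and potentially clinically significant will be flagged and tabulated".

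**The concern.** A limit for a marked abnormality should be crossed rarely without a drug effect. The HDL band is only 20 mg/dL wide and two-sided, and the counting rule takes no account of where the subject started. A subject with HDL 62 mg/dL before and after dosing counts as an event. If many subjects sit outside 40–60 mg/dL anyway, the laboratory percentage mostly describes the HDL levels subjects brought into the study.

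The placebo arm offers little help. It has 4 subjects, so one subject is 25 percentage points, and Part 2 has no concurrent control. Protocol 4.1 describes TAK-935 as inhibiting an enzyme that metabolises cholesterol, so lipids are a panel on which a real change should be readable.

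The AAG gap is a different kind of problem: the SAP does not give the limit in the units in which it says it will analyse the data.

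**Working it through.** **1. Are the two HDL rows the same band?** The LDL upper limits (160 mg/dL, 4.14 mmol/L) imply a factor of 4.14/160 = 0.025875. Then 40 × 0.025875 = 1.035 (stated 1.04) and 60 × 0.025875 = 1.5525 (stated 1.55). The rows agree, so the band is not a slip in one cell.

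**2. How narrow is it?** Upper limit divided by lower limit:

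| Test | Limits (mg/dL) | Ratio |
|---|---|---|
| HDL | 40–60 | 1.5 |
| LDL | 50–160 | 3.2 |
| Glucose | 50–350 | 7.0 |

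**3. How many post-dose draws are there?** Protocol Appendix A schedules laboratory tests at Screening and on Days 1, 31 and 85. Day 31 is the post-dose draw for Part 1 and, taken before the first open-label dose, the baseline for Part 2. Day 85 is the post-dose draw for Part 2. That is one scheduled post-dose draw per part and two for the combined summary in SAP 7.11.

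**4. Flag rate with no drug effect.** Assumptions, none from the documents: HDL is normal with mean m and SD s; the two draws have within-subject correlation 0.8; all 16 TAK-935 subjects are sampled.

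One draw: P = Φ((40 − m)/s) + 1 − Φ((60 − m)/s). For m = 50, s = 10: 0.159 + 0.159 = 0.317. For m = 45, s = 15: 0.369 + 0.159 = 0.528.

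Either of two draws: 1 − P(both within 40–60) under the bivariate normal.

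| Mean | SD | One draw | Of 16 | Either of two | Of 16 |
|---|---|---|---|---|---|
| 50 | 6 | 9.6% | 1.5 | 14.4% | 2.3 |
| 50 | 10 | 31.7% | 5.1 | 43.9% | 7.0 |
| 50 | 15 | 50.5% | 8.1 | 66.4% | 10.6 |
| 45 or 55 | 10 | 37.5% | 6.0 | 49.7% | 8.0 |
| 45 or 55 | 15 | 52.8% | 8.4 | 68.3% | 10.9 |

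Unscheduled samples can only raise these rates.

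**5. Does HDL dominate the count?** Let HDL flag a share p and all other tests a share q, independently (assumed). The composite is 1 − (1 − p)(1 − q), and the share of flagged subjects flagged by HDL alone is p(1 − q)/composite.

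- p = 0.40, q = 0.05: composite 1 − 0.60 × 0.95 = 0.43; HDL-only share 0.38/0.43 = 88%.
- p = 0.40, q = 0.20: composite 1 − 0.60 × 0.80 = 0.52; HDL-only share 0.32/0.52 = 62%.
- p = 0.05, q = 0.20: composite 1 − 0.95 × 0.80 = 0.24; HDL-only share 0.04/0.24 = 17%.

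Dominance therefore depends on the inputs.

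**6. Can placebo calibrate it?** With a true background of 32%, the chance that none of 4 placebo subjects is flagged is 0.68⁴ = 0.21. A placebo rate of 0% would appear about one time in five.

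**7. AAG.** If the preferred SI unit is g/L (not stated), 1 mg/dL = 0.01 g/L, so 47 and 125 mg/dL become 0.47 and 1.25 g/L. This supplies the missing row without changing which values are flagged.

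**The case against.** The strongest reply is that every percentage above rests on an assumed distribution. The documents give no HDL distribution, no HDL or AAG reference range and no expected MAV rate for the other tests. That stands: a reader might infer that HDL will dominate the endpoint, but the documents support only that it is likely to inflate it and may dominate it.

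The two-draw figure also fits only the combined summary. For the by-part summaries the one-draw figure applies.

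A reader might also infer that the endpoint cannot reveal a drug effect on laboratory values. The documents do not support this. The analysis is descriptive, results are shown by treatment, change from baseline is summarised, all visits are listed for any flagged parameter, and flagged subjects are mapped. HDL-driven flags can be traced. The headline percentage is inflated all the same.

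For AAG, a reader might infer that every subject would be flagged low, because g/L values would be compared with 47. That would need a programming error: the limit is labelled as conventional and in mg/dL, and for results SAP 7.11.2 says "the conversion to SI units will be done in derived analysis data sets using the known conversion factors". The gap is one missing row.

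Deliberate two-sided lipid limits are plausible for this mechanism, and LDL has them too. Whether high HDL matters for safety, and whether 47–125 mg/dL is an ordinary AAG range, cannot be settled from the documents. Protocol 13.1.3.2 suggests two tiers, but it does not say that MAV is the stricter one, and SAP 7.11.2 defines no out-of-range table to which HDL could be moved. Deleting HDL and AAG from the count outright would therefore go too far.

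**Conclusion.** The concern holds for HDL as a likely inflation of the laboratory MAV percentage. Two facts come from the text alone: the band is narrow compared with the rest of Appendix A, and the rule counts values already outside it before dosing. The size is conditional. It is about 5–8 of 16 TAK-935 subjects per part and 7–11 of 16 for both parts combined under a mean of 45–55 and SD of 10–15 mg/dL. It falls to about 2 of 16 on either basis if HDL is tightly centred (mean 50, SD 6). With 4 placebo subjects, the trial cannot tell which of these backgrounds applies.

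The missing AAG SI row is a real but separate and smaller specification gap. It adds nothing to the estimated inflation.

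**What to change.** In the SAP:

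1. Check the HDL limits, especially the upper one, and the AAG limits against the sponsor's predefined MAV criteria. Revise them if they turn out to be reference-type limits; otherwise state the reason for keeping them.
2. Add the AAG SI row (0.47 and 1.25 g/L if the preferred unit is g/L).
3. Tabulate laboratory MAVs by parameter, separating those already present at baseline from those new after dosing. Appendix C already uses a change condition in one QTcF criterion, so the idea is not foreign to this SAP.
4. Report the percentage with at least one laboratory MAV as planned and also without HDL and AAG. Keep both tests visible in the by-parameter tables.

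The cost is SAP wording and slightly more tabulation. No new data are needed. The additional count will show a lower headline percentage than the planned one, so the report should explain the difference.

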**Appendix B Criteria for Markedly Abnormal Vital Signs**

Parameter	Unit	Lower Criteria	Upper Criteria
Pulse	bpm	<50	>120
Systolic blood pressure	mm Hg	<85	>180
Diastolic blood pressure	mm Hg	<50	>110
Body temperature	°C	< 35.6	>37.7

### Appendix C Criteria for Markedly Abnormal 12-Lead ECG Parameters

Parameter	Unit	Lower Criteria	Upper Criteria
Heart Rate	bpm	< 50	> 120
PR	msec	$\leq 80$	$\geq 200$
RR	msec	$\leq 600$	$\geq 1440$
QRS	msec	$\leq 80$	$\geq 180$
QT Interval	msec	$\leq 50$	$\geq 460$
QTcF Interval	msec	$\leq 50$	$\geq 500$ OR $\geq 30$ change from baseline and $\geq 450$

ELECTRONIC SIGNATURES

Signed by	Meaning of Signature	Server Date (dd-MMM-yyyy HH:mm 'UTC')
PPD	Biostatistics Approval	31-Oct-2018 13:35 UTC
	Clinical Approval	31-Oct-2018 13:51 UTC
	Biostatistics Approval	01-Nov-2018 15:55 UTC
